7.7 Serious AE Reporting

Serious AEs occurring after the patient has provided informed consent, but before the first dose of study treatment, will be collected as medical history unless the event is either new and attributed to protocol-mandated procedures by the Investigator or there is a significant change in the rate of occurrence or an increase in the severity of the pre-existing condition which is judged to be clinically important and attributed to the protocol-mandated procedures by the Investigator. Any new or clinically significant changes in the patient's medical that occur after the first dose of drug and meet the SAE criteria will be recorded as SAEs.

All SAEs, regardless of causality, with an onset within 30 days after the last dose of study drug(s) will be reported to Nektar Therapeutics Drug Safety immediately without undue delay, under no circumstances later than 24 hours following knowledge of the event.

In addition, SAEs that are assessed by the Investigator as related to study drug(s) and occurring after the SAE reporting period will also be reported to Nektar Therapeutics Drug Safety immediately without undue delay, under no circumstances later than 24 hours following knowledge of the event.

SAEs must be reported to Nektar Therapeutics Drug Safety via email or Fax as listed at the beginning of this protocol. Nektar Therapeutics may transition to reporting of SAEs via EDC while the study is ongoing. If this occurs, all sites will receive documented instructions regarding how to enter SAEs into EDC. If the study were to transition to reporting of SAEs in EDC, sites would continue to submit SAEs via email or Safety Fax as a backup system should there be EDC system access issues.

The Investigator must complete the SAE Report Form, assess the causality relationship to the study treatment as applicable, and send the completed SAE form via email or fax to Nektar Therapeutics Drug Safety. A follow-up report and any additional records (such as hospital records, consultant reports, and autopsy findings) will be emailed or faxed to Nektar Therapeutics Drug Safety immediately without undue delay, under no circumstances later than 24 hours following knowledge of the follow-up information. Any medication or other therapeutic measures used to treat the event will be recorded.

All SAEs will be followed as described in Section 7.8.

Reporting of SAEs to the IRB/IEC will be done in accordance with the standard operating procedures (SOPs) and policies of the IRB/IEC. Adequate documentation must be provided to Nektar Therapeutics showing that the IRB/IEC was properly notified. Serious AEs will be reported by Nektar Therapeutics or designee to the Regulatory Authorities per local regulations.

7.8 Serious AE Follow-up

All study treatment-related SAEs that have not resolved by the Safety Follow-Up call will be followed until any of the following occur (whichever comes first):

- The event resolves.
- The event has stabilized.
- The event returns to baseline, if a baseline value is available.
- It is unlikely that any additional information can be obtained (eg, patient or health care practitioner refuses to provide additional information; lost to follow-up after demonstration of due diligence with follow-up efforts).
- The patient dies or is lost to follow-up.

All ongoing SAEs will be followed until resolution or until the Safety Follow-Up call, whichever is earlier. In the case where an SAE has not completely resolved by the Safety Follow-Up call, the final outcome of these ongoing SAEs will be captured as "Not Recovered/Not Resolved" or "Recovering/Resolving", whichever is applicable.

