5.7 Safety Follow-up

The Safety Follow-Up telephone call should occur 30 days (\pm 7 days) after discharge from the hospital or in-patient facility as described in Section 1.2. If a patient remains at the inpatient facility after Day 8, the Safety Follow-Up call should occur no later than 38 days (\pm 7 days) after Day 1, the day of study drug administration.

Collection of samples for immunogenicity, DNA/RNA sequencing, SARS-CoV-2 serology, immune cell profiling, and detection of SARS-CoV-2 nucleic acid should occur 30 days

 $(\pm 7 \text{ days})$ after discharge from the hospital or in-patient facility as described in Section 1.2. If a patient remains at the in-patient facility after Day 8, samples should be collected no later than 38 days ($\pm 7 \text{ days}$) after Day 1, the day of study drug administration. If the patient is unable to return to the clinic, samples may be collected by research staff or designee at an alternate location.

The patient will be followed for safety until resolution or permanent sequelae of all toxicities attributable to study drug as outlined in Sections 7.5 and 7.8. If the patient discontinues study drug for a clinically significant AE, the patient will be followed until resolution of the AE or the event is considered to be stable and/or chronic.

For AE and SAE reporting periods, please refer to Sections 7.5 and 7.7.

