9.2 Determination of Sample Size

This Phase 1b study will assess the safety and tolerability of different doses of bempegaldesleukin. No formal sample size calculation is done. Around 10 patients per dose cohort with a 1:1 randomization ratio (5 bempegaldesleukin/SOC and 5 placebo/SOC) to bempegaldesleukin/SOC or placebo/SOC will be enrolled.

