9.5 Safety Analyses

The safety analyses will be based on the Safety population. For patients who receive placebo, the safety data will be pooled. Treatment-emergent AEs (TEAEs) will be defined as AEs that occur on or after receiving the first dose of study drug. The frequency of TEAEs will be tabulated using the Medical Dictionary for Regulatory Activities (MedDRA) by system organ class and preferred terms and treatment. In addition, by patient listings will be provided for TEAEs and SAEs.

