11.2 Adverse Events

An AE is defined as any untoward medical occurrence in a subject who is administered a medicinal product and that does not necessarily have a causal relationship to the treatment. All AEs will be included in the data listings. Verbatim terms on case report forms will be mapped to preferred terms and system organ classes (SOC) using the Medical Dictionary for Regulatory Activities (MedDRA) (version 20.0).

A Treatment-Emergent Adverse Event (TEAE) is defined as an adverse event that occurs on or after the treatment dose, and treatment-emergent period is from the study dose date to 30 days after the study dose. The TEAE summary will be displayed by treatment using treatment-emergent period. Unless otherwise specified, summaries that are displayed by SOC and preferred terms will be ordered alphabetically by SOC, and within each SOC, preferred terms will also be ordered alphabetically. Summaries of the following types will be presented:

- TEAEs by MedDRA SOC and preferred term.
- TEAEs by MedDRA SOC, preferred term, and worst CTCAE grade (version 5.0). At each level of subject summarization, a subject is classified according to the worst CTCAE grade if the subject reported one or more CTCAE grade.
- TEAEs related to study drug by MedDRA SOC, preferred term, and worst CTCAE grade.
- TEAEs by descending incidence of preferred terms.
- Serious TEAEs by MedDRA SOC, preferred term and worst CTCAE grade.
- Serious TEAEs related to study drug by MedDRA SOC, preferred term, and worst CTCAE grade.
- TEAEs leading to early termination by MedDRA SOC, preferred term, and worst CTCAE grade.
- Any Grade \geq 3 drug-related AE.
- Respiratory compromise or other virus-related AE attributed to worsening COVID-19, such as severe hypoxia, cyanosis, or chest pain/pressure.
- TEAEs leading to deaths.

For each subject and for each adverse event, the duration of the event (days) will be calculated as:

Duration of AE (Days) = AE stop date - AE start date +1.

The duration of AEs will be displayed in the data listing.

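### Protocol 7.8 gives two follow-up rules for treatment-related SAEs, and SAP 11.2 narrows the TEAE definition of Protocol 9.5 without declaring it

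*Protocol*

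**What the plan says.** **Follow-up of SAEs.** The first paragraph of Protocol 7.8 reads: "All study treatment-related SAEs that have not resolved by the Safety Follow-Up call will be followed until any of the following occur", and a list of end points follows (resolution, stabilization, return to baseline, no further information obtainable, death or loss to follow-up). The last paragraph of the same section reads: "All ongoing SAEs will be followed until resolution or until the Safety Follow-Up call, whichever is earlier". For an SAE still open at the call it adds that "the final outcome of these ongoing SAEs will be captured as" not recovered or recovering. Neither sentence of that paragraph is limited by relationship to study drug.

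Protocol 5.7 says: "The patient will be followed for safety until resolution or permanent sequelae of all toxicities attributable to study drug", and refers to 7.5 and 7.8 for the details. Protocol 7.5, the parallel section for all AEs, fixes the outcome at the call only for events not related to study drug. It follows related events until they resolve or are judged stable.

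**Definition of a TEAE.** Protocol 9.5: "Treatment-emergent AEs (TEAEs) will be defined as AEs that occur on or after receiving the first dose of study drug". No end date is given. SAP 11.2 also starts from dosing but adds that the "treatment-emergent period is from the study dose date to 30 days after the study dose", and it builds the TEAE summary on that period. SAP 12.0 states that no change from the protocol's analyses is planned.

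**Collection of later events.** Protocol 7.7: "SAEs that are assessed by the Investigator as related to study drug(s) and occurring after the SAE reporting period will also be reported". Protocol 7.5 also captures new AEs after the call if they are related to study drug.

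**The concern.** A site that applies the last paragraph of 7.8 literally would stop following a related SAE at the call and record its outcome as unresolved. Under 7.5 it would go on following a related non-serious AE until that event resolved or became stable. The more serious event would get the shorter follow-up, and its true outcome might never be recorded.

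The tabulation problem is different. The protocol arranges to receive related SAEs after the 30-day reporting period and counts them as treatment-emergent. The SAP's window excludes them from the serious-TEAE tables, which serve the secondary objective on SAE frequency. A reader of the SAP would not know this differs from the protocol, because SAP 12.0 says nothing differs.

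**Working it through.** There is no planned figure to reproduce. Protocol 9.2 says "No formal sample size calculation is done", and the point does not depend on power or error rates. The check is a comparison of texts plus calendar arithmetic.

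**Step 1: a related SAE still open at the call**

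| Source | What happens |
|---|---|
| Protocol 7.8, first paragraph | Follow-up continues past the call |
| Protocol 7.8, last paragraph | Follow-up stops and the outcome is fixed |
| Protocol 7.5 | Follow-up continues until resolved or stable |
| Protocol 5.7 | Follow-up continues until resolution or permanent sequelae |

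Three rules agree and one does not. Section 7.7 cannot settle the matter, because for follow-up it refers back to 7.8.

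**Step 2: a related SAE with onset after the SAP window**

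| Source | What happens |
|---|---|
| Protocol 7.7 | Reported to the sponsor, with no end date |
| Protocol 9.5 | Is a TEAE |
| SAP 11.2, listings | Listed, since all AEs are listed |
| SAP 11.2, TEAE, serious-TEAE and TEAE-leading-to-death tables | Left out |
| SAP 11.2, drug-related Grade 3 or higher summary | May be counted if of that grade; this summary is not labelled TEAE |

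**Step 3: the gap between the end of the window and the call**

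Inputs: dosing is Day 1 (SAP 5.1); the SAP window is dosing + 30 days; the call is 30 ± 7 days after discharge (Protocol 1.2 and 5.7). After a stay beyond Day 8, the call comes no later than 38 ± 7 days after Day 1.

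- Last day of the SAP window: 1 + 30 = Study Day 31.
- Discharge on Day 8: call on 8 + 30 = Day 38, range 38 − 7 = 31 to 38 + 7 = 45. Gap: 38 − 31 = 7 days, range 0 to 14.
- Stay beyond Day 8: latest call on 1 + 38 = Day 39, range 32 to 46. Gap: 8 days, range 1 to 15.
- Discharge on Day 2 (an assumed example of early discharge): call on 2 + 30 = Day 32, range 25 to 39. Gap: 1 day, from 6 days before the window closes to 8 days after.

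The call is the last scheduled contact at which such an event would be found. Related SAEs that come to light later still are also reportable under 7.7 and also outside the window.

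**Step 4: the weight of one omitted patient**

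- One dose group: 1/5 = 20%.
- All active patients, if three cohorts fill as planned (3 × 5 = 15): 1/15 = 6.7%.

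**The case against.** The strongest case has four parts.

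- **Section 7.8 can be read as consistent.** The first paragraph would be a specific rule for related SAEs and the last a general rule for the rest. Section 7.5 has the same structure: an unqualified sentence ending follow-up at the call, then separate treatment of related events. A related SAE is also an AE, so 7.5 requires continued follow-up anyway. This is probably what was intended. It does not remove the defect: 7.5 limits its outcome sentence to unrelated events and 7.8 does not, so each site has to infer the exception.
- **Thirty days is not arbitrary.** It matches the general AE reporting period (Protocol 5.13, 7.2 and 7.5) and the all-causality SAE period (7.7), and Protocol 9.1 leaves detailed methods to the SAP. That supports 30 days for events of any cause. It does not cover the related events that the protocol collects beyond it, nor the statement in SAP 12.0.
- **Late related events should be rare.** One dose is given, the half-life is about 20 hours, and Protocol 5.3.2.1 expects drug-related AEs mostly 1 to 5 days after treatment. This stands, and it is the main reason to rate the point as minor.
- **The data are not lost.** Late events are listed, and those of Grade 3 or higher may enter the drug-related summary. Death is a reason for study discontinuation in Protocol 5.8, and SAP 7.1 tabulates those reasons, so an on-study death reaches the disposition table. This also stands.

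A reader might therefore go too far in three ways. One might infer that 7.7 is contradicted; it governs reporting, and neither 7.8 nor the SAP window stops a report. One might infer that late related events would appear in a listing and nowhere else; the Grade 3 or higher summary and the disposition table show otherwise. One might infer that 7.8 distorts SAE frequency; frequency counts occurrences, and the SAP plans no table of SAE outcomes.

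**Conclusion.** Both parts hold, as separate points.

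1. Protocol 7.8 contradicts itself, and its last paragraph conflicts with 5.7 and 7.5. The consequence is limited to how long related SAEs are followed and what outcome is recorded. It applies to any related SAE open at the call, whenever it began.
2. SAP 11.2 is narrower than Protocol 9.5, and SAP 12.0 is incorrect in saying that nothing changed. Related SAEs with onset after Study Day 31 are collected but left out of the TEAE, serious-TEAE and TEAE-leading-to-death tables.

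For the planned Day 8 discharge, the call is nominally 7 days after the window closes (0 to 14). The 20% figure for one patient in a dose group assumes that five patients receive active drug at that dose and that one such event occurs. The documents give no rate for events this late and lead one to expect few. The severity is minor, but this is a rule that is wrong as written rather than a missing detail.

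**What to change.** **Protocol 7.8.** Reconcile the two paragraphs by limiting both sentences of the last one, the follow-up sentence and the outcome sentence, to SAEs not related to study drug. A qualifier in the outcome sentence alone, which is where 7.5 has it, would leave the conflicting follow-up sentence unchanged.

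**SAP 11.2.** Count as TEAEs all AEs with onset within 30 days of dosing, plus any later AE or SAE judged related to study drug. Tabulate all reported deaths, whatever their timing or cause.

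**SAP 12.0.** Declare any remaining difference from Protocol 9.5. One would remain: an unrelated AE recorded with onset after Study Day 31 is a TEAE under 9.5 but not under this definition. Making late TEAE status depend on causality is one workable choice, chosen because it matches what the protocol collects after 30 days. If the sponsor prefers the plain 30-day limit, SAP 12.0 should say so and the SAP should state how later related SAEs are summarized.

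The cost is one qualifying phrase, applied to two sentences of the protocol, and a sentence or two in the SAP. No new data are collected.

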7.9 Adverse Events of Special Interest

Cytokine release syndrome (CRS) is considered an "adverse event of special interest" (AESI) and should be assessed for seriousness using the standard seriousness definition. However, all CRS events are required to follow the process and timeline for SAE reporting (within 24 hours as described in Section 7.7) from the sites to Nektar Drug Safety: [contact]. Grading criteria for CRS are provided in Appendix 3.

7.10 Potential Drug-Induced Liver Injury

Wherever possible, timely confirmation of initial liver-related laboratory abnormalities should occur prior to the reporting of a potential drug-induced liver injury (DILI) event. All occurrences of potential DILIs, meeting the defined criteria, must be reported as SAEs (see Section 7.7 for reporting details). A potential DILI is defined as:

• Treatment-emergent ALT or AST > 3 times ULN.

AND

• Total bilirubin > 2 times ULN or clinical jaundice, without initial findings of cholestasis (eg, elevated serum alkaline phosphatase > 2 times ULN).

AND

• No other immediately apparent possible causes of elevated liver enzymes and hyperbilirubinemia, including, but not limited to, viral hepatitis, pre-existing chronic or acute liver disease, or the administration of other drug(s) known to be hepatotoxic.

7.11 Pregnancy Tests/Pregnancy

7.11.1 Pregnancy Tests

Serum or urine pregnancy tests will be performed on WOCBP according to the Schedule of Events (Section 1.2). Urine pregnancy tests should have a minimum sensitivity of 25 IU/L or equivalent units of HCG. A negative pregnancy test result must be obtained before the administration of the study drug(s) and on the day of hospital discharge.

A pregnancy test does not need to be performed on women who are postmenopausal (see Appendix 2) for at least 1 year or surgically sterile for at least 3 months before signing the ICF.

If a female patient becomes pregnant, administration of the study drug(s) must be discontinued immediately. Requirements for reporting a pregnancy are provided in Section 7.11.2.

If, for whatever reason, the pregnancy has ended, confirmed by a negative serum pregnancy test, treatment may be resumed at the discretion of the Investigator (at least 3 weeks and not greater than 6 weeks after the pregnancy has ended) following approvals of the patient/IRB/EC, as applicable.

7.11.2 Pregnancy

7.11.2.1 Pregnancies in Female Patients

The Sponsor must be notified immediately without undue delay, under no circumstances later than 24 hours following knowledge of the initial report and any follow-up reports of a female patient becoming pregnant during the course of the study. All reports should be submitted via the Pregnancy Notification Form. Pregnancy, although reportable, is not considered an AE/SAE unless a female patient experiences signs or symptoms of pregnancy complications; however, the contact information for pregnancy reporting is the same as for SAE reporting and listed in Section 7.7. Female patient(s) who become pregnant will be followed until the outcome of the pregnancy is known. Pregnancy follow-up should describe the outcome of the pregnancy, including any voluntary or spontaneous termination, details of the birth, and the presence or absence of any congenital abnormalities or birth defects in the offspring.

If a female patient becomes pregnant, administration of the study drug(s) must be discontinued immediately.

7.12 Clinical Laboratory Tests

Clinical laboratory tests will be conducted at both a local laboratory and central laboratory according to the Schedule of Events (Section 1.2). A list of the clinical laboratory analytes to be tested is provided in Appendix 1. Local lab samples should be collected according to the Schedule of Events and the local lab will perform the tests listed in Appendix 1A. Central lab samples should be collected according to the Schedule of Events and the local go to the Schedule of Events and the central lab will perform the tests listed in Appendix 1A.

the tests listed in Appendix 1B. All blood samples collected for central lab processing will be collected and sent to the central laboratory on the day of collection unless otherwise instructed.

For enrollment, if the central laboratory tests are cancelled, lost, unavailable, or considered inadequate for analysis, the site may forward an identical set of local laboratory results for eligibility review (with central laboratory testing repeated prior to the first dose of study drug). If local laboratory results are determined to be acceptable during eligibility review, enrollment may proceed.

Clinical laboratory test data will be reviewed by the Investigator or Sub-Investigator. Additional clinical laboratory tests may be ordered at the Investigator's or Sub-Investigator's discretion.

The Investigator or Sub-Investigator will review all laboratory results for clinical significance. Any laboratory result deemed clinically significant (ie, is associated with signs and symptoms, requires treatment, or requires follow up) will be recorded as an AE as described in Section 7.1.

7.13 Physical Examinations

Physical examinations should be conducted according to the Schedule of Events (Section 1.2). Full physical examinations should be conducted at screening, and prior to dosing (evaluate all major organ systems, including the following categories: general, head, eyes, ears, mouth/throat, neck, heart, lungs, abdomen, lymph nodes, joints, extremities, integumentary, neurologic, and psychiatric). Other examinations may be targeted, at the discretion of the Investigator, to identify changes from baseline or evaluate changes based on the patient's clinical symptoms.

7.14 Vital Signs

Vital sign measurements will be recorded according to the Schedule of Events (Section 1.2). Vital signs include pulse rate, respiratory rate, systolic and diastolic blood pressure, oxygen saturation, and temperature. It is preferred that the same arm be used for all blood pressure readings, if possible. Weight is to be reported at screening and on the day of dosing, height at screening visit only.

7.15 Electrocardiograms

All patients will have 12-lead electrocardiogram (ECG) done during Screening as specified in the Schedule of Events (Section 1.2). ECG data will be locally assessed. After enrollment, the frequency of ECGs may be increased if clinically indicated.

7.16 Cohort Review Committee

A Cohort Review Committee (CRC) consisting of representatives from the Sponsor's Clinical Development, Drug Safety, Biostatistics, and other functional representatives as needed, and at least one Principal Investigator will meet to review safety and tolerability data, review the safety profile in the first 72 hours after study drug administration in the sentinel patients at the

beginning of each cohort, adjudicate AEs reported as DLTs, make decisions about escalating or de-escalating the dose of bempegaldesleukin, and identify the RP2D.

